### 5.4 Exclusion Criteria

- Chronic systemic steroid use, including inhaled compounds, or any medication which can alter glucose metabolism
- Treated with any other oral or injectable hyperglycemic medication other than insulin.
- Obesity, defined as BMI >95 percentile, or BMI >27 in adolescents with acanthosis score between 1-1.5
- Pregnant and/or breastfeeding
- History of seizure disorder (epilepsy, head trauma, cerebral vascular accident), or any clinical features of continuous motor unit activity in proximal muscles
- Patients on medications which may disturb GABA action, such as Baclofen, Valium, Acamprosate, Neurontin, or Lyrica
- History of alcoholism or any substance abuse
- Chronic disease (such as liver, cancer, cystic fibrosis, or renal failure)
- Chromosome abnormality (such as trisomy 21, Turner Syndrome,..etc)
- History of anemia, or significantly abnormal hemoglobin results at screening
- Clinically significant history of acute reaction to vaccines and other drugs in the past.
- Known history of HIV or hepatitis
- Unwillingness to comply with conditions of the protocol
- History of illness, besides diabetes within 2 weeks of first GAD-alum/placebo injection
- Any condition that the PI feels would not be beneficial for the subject to be on study.

5.5 *Informed Consent:*

Potential participants will be approached by research personnel during initial hospitalization for new onset Type I Diabetes at The Children’s Hospital of Alabama to provide information regarding the study. If interested, the informed consent document will be provided to the potential participant and contact information will be provided for study personnel. Subjects choosing to participate will be asked to consent for study participation prior to, or at the first clinic visit post diagnosis. Before the first follow up clinic appointment at one month, written consent from the parents and patient 14 years or older, or assent from children aged 7-13, will be obtained in a quiet setting prior to the initiation of any study procedures. Patients will not be consented in writing until they are able to demonstrate adequate understanding of all aspects of the study and consent process. A copy of the consent form will be given to the patient. The signed consent form remains in the patients study files at the clinical center. Consented participants will then be randomized

5.6 *Randomization:*

A total of 110 patients, with 30 in the GABA + GAD-alum group 43 in the GABA + placebo GAD-alum group, and 37 in the placebo GABA and placebo GAD-alum group will be enrolled. The study will be double-blinded with randomization under the stewardship of the Children’s Hospital research pharmacist. Subjects will be randomized to one of the three treatment groups in a 1:1:1 ratio using a pre-set randomization list (generated by using a computerized procedure) known only to the un-blinded pharmacist.

The patients will be followed for a total study period of 12 months which includes 5 visits to the clinic.

See table 1 below for an overview of randomization groups and study visits.

**Table 1. Randomization and study visits**

Study	Day 1 Baseline Randomization	Mo 1	Mo 5	Mo 8	Mo 12
	Visit 1 <5 weeks from diagnosis	Visit 2 ± 7	Visit 3 ± 7	Visit 4 ± 7	Visit 5 ± 7
Group 1 GABA-GAD group (GABA+GAD-alum)  30 subjects	GABA twice daily, every day from Baseline to Month 12				
	Prime injection GAD-alum 20 µg	Boost injection GAD-alum 20 µg			
Group 2  GABA group ( GABA+ Placebo GAD-alum)  43 subjects	GABA twice daily, every day from Baseline to Month 12				
	Prime injection Placebo GAD-alum	Boost injection Placebo GAD- alum			
Group 3  Placebo group (Placebo GABA + Placebo GAD-alum)  37 subjects	Placebo GABA twice daily, every day from Baseline to Month 12				
	Prime injection Placebo GAD-alum	Boost injection Placebo GAD- alum			

5.7 *Treatment Doses and Schedule*

- 1) Oral Gamma-Aminobutyric Acid (GABA)

We shall not exceed the recommended adult dosages (up to 1.5 grams/day) and we will adjust the dose to the body surface area of the children enrolled in our study. For example, the average adult has a body surface area of 1.5 - 2 m^2. Therefore, the current recommended adult dosage is equivalent to 1 grams/m^2/day, and this is the dose we will be giving to our trial participants. This total daily amount will be divided in two daily doses to be given with breakfast and dinner. The GABA will be supplied by the manufacturer NOW Foods in 200 mg capsules. Each dose will be rounded to the nearest 100 mg. The placebo will also be provided by NOW Foods and will be indistinguishable in appearance, taste, and smell from the GABA capsules. The capsules will be opened and dissolved in water, or sprinkled on food immediately before consumption. Documentation of these products by site personnel will be documented in the case report form (CRF).

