Study Design: The study is a 3-arm, randomized, double-blind, placebo-controlled, clinical trial. Patients will receive either 
 
i) oral GABA, dosed per kg, twice daily for 12 months plus 2 subcutaneous injections of 20 µg Diamyd in a prime-and-boost regimen over a period of 30 days
 
ii) oral GABA, dosed per kg, twice daily for 12 months, Placebo GAD-alum 2 subcutaneous injections over a period of 30 days.
 
iii) placebo.
 
 
The patients will be followed for a total of 12 months.

Selection of Subjects: Patients must be age 4 to 18years old, and diagnosed with Type 1 Diabetes (T1D) within the previous 5 weeks of randomization. Patients must be positive for GAD-65 autoantibody to be enrolled. They may, or may not be positive for the other autoantibodies at the time of enrollment, but all will be followed during the study.
Number of Subjects Planned: Approximately 110 patients will be enrolled.
Description of Treatment Groups: The patients will be assessed for eligibility prior to randomization. On Visit 1 (Day 1, baseline), patients eligible for the study will be randomized to 1 of 3 treatment groups: 
 
• 30 patients will be assigned to receive oral GABA twice daily, dosed per kg, from Day 1 through Month 12. In addition 2 subcutaneous injections with 20 µg Diamyd (GAD-alum) will be given at Day 1 and Month 1, i.e., 1 prime and 1 booster dose (providing a total dose of 40 µg Diamyd).
 
• 43 patients will be assigned to receive oral GABA twice daily, dosed per kg, from Day 1 through Month 12. In addition 2 subcutaneous injections with Placebo GAD-alum will be given at Day 1 and Month 1
 
• 37 patients will be assigned to receive oral Placebo GABA twice daily, dosed per kg, from Day 1 through Month 12. In addition 2 subcutaneous injection with Placebo GAD-alum will be given at Day 1 and Month 1
 

Name of Sponsor [name]
Name of Finished Product: GABA (Gamma-Aminobutyric Acid) DIAMYD® 20µg, subcutaneous injection (GAD-alum)
Name of Active Ingredient: Gamma-Aminobutyric Acid (GABA) Recombinant Human Glutamic Acid Decarboxylase (rhGAD65)

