#### 6.7 Data Collection and Assays:

Subject visits will consist of a baseline visit and subsequent visits as noted above. The data noted in the table above will be collected by study personnel and stored in a locked office and on a password-protected UAB computer. All laboratory specimens will be collected by study personnel, labeled with the study participant's unique identifier and date of collection, and then stored at -80°C in [name] lab. Analysis of all laboratory measurements will be completed at the conclusion of the study.

- 1.) *Hemoglobin A1C*: Measured by latex immunoagglutination inhibition methodology( DCA 2000, Siemens-Bayer)
- 2.) *Mixed Meal Tolerance Test*: After an overnight fast, the patients will have an IV placed and will drink Boost. They will have C-peptide and glucose and glucagon levels drawn at 10 minutes prior to dose (-10), 0, 15, 30, 60, 90, and 120 min. The C-peptide, glucagon, and glucose levels will be assayed by the UAB Metabolism Core of the Clinical Nutrition Research Center (CNRC). At the 1 and 5 month visits, only a fasting and 90 minute sample are obtained. A recent 2013 article confirms that this 90- minute sample alone correlates significantly with the integral of the C- peptide as a function of time curve, oft-called the AUC [21].
- 3.) *Pancreatic Antibodies*: GAD-65, ICA512 and Anti-Zinc Transporter 8 samples are collected as standard of care at initial diagnosis. We will use these results as our baseline. Follow-up samples will be collected at the visits noted in the Table. Samples will be assayed at ESOTERIX Laboratory Services, Inc..
- 4.) *CBC with manual differentiation*: Performed at baseline and at the visits noted in the Table, and assayed in the hematology lab of Children's Hospital Alabama

- 5.) *Complete Metabolic Profile*: CMP will be monitored at the visits noted in the Table, and assayed in the chemistry lab of Children's Hospital Alabama.
- 6.) *Glucagon*: Glucagon levels will be measured under fasting conditions at the visits noted in the Table, and during the Mixed Meal Tolerance Tests. Assays will be conducted by UAB Metabolism Core of the Clinical Nutrition Research Center (CNRC).
- 7.) *Height*: Collected at each visit
- 8.) *Weight*: Collected at each visit to make dosing adjustments in the GABA .
- 9.) *Medications*: We will review total daily insulin dose and compliance. We will review all other non-study medications which the patients are taking.

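### GABA is dosed per kg in the Synopsis but by body surface area in Section 5.7, and above 1.5 m² the 1 g/m²/day dose and the 1.5 g/day limit cannot both hold

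*Combined protocol and SAP*

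**What the plan says.** The Synopsis, under Study Design, describes the combination arm as "oral GABA, dosed per kg, twice daily for 12 months plus 2 subcutaneous injections", and the GABA-only arm likewise. Under Description of Treatment Groups the per-kg basis appears again for both active groups ("patients will be assigned to receive oral GABA twice daily, dosed per kg, from Day 1 through Month 12") and for placebo GABA. No mg/kg value is given there or elsewhere.

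Section 5.7 (Treatment Doses and Schedule) uses another basis: "We shall not exceed the recommended adult dosages (up to 1.5 grams/day) and we will adjust the dose to the body surface area". It takes 1.5 to 2 m² as the adult surface area, treats the adult dosage as equivalent to 1 g/m²/day, and adds "and this is the dose we will be giving to our trial participants". The daily amount is split into two doses, and each dose is rounded to a multiple of 100 mg.

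Section 6.7, item 8, gives the purpose of recording weight: "Collected at each visit to make dosing adjustments in the GABA". Item 7 records height at each visit without linking it to dosing. Section 5.3 admits participants aged 4 to 18.

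**The concern.** Three things do not fit together.

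- **Dosing basis.** Surface area per kilogram falls as a child grows. A per-kg rule and a per-m² rule therefore cannot agree across ages 4 to 18, and nothing in the protocol connects them.
- **Limit against dose.** Section 5.7 sets a daily maximum and then names a per-m² dose that passes it for anyone above 1.5 m². It does not say which statement gives way.
- **Rounding.** The rounding rule does not fit the stated maximum.

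Both objectives in Section 4.1 concern the safety and effect of GABA in this age range. Without one consistent rule, staff have no clear instruction for adult-sized adolescents, and a reader cannot describe or reproduce the regimen from the protocol. Section 9.0 plans no exposure summary that would show afterwards what was dispensed.

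**Working it through.** **Inputs from Section 5.7:** limit 1.5 g/day; adult surface area 1.5 to 2 m²; dose 1 g/m²/day; two doses a day, each rounded to a multiple of 100 mg.

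**Step 1. The plan's own equivalence.** Dose per m² = 1.5 g/day ÷ area.

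- 1.5 ÷ 1.5 = 1.00 g/m²/day
- 1.5 ÷ 1.75 = 0.857 g/m²/day
- 1.5 ÷ 2.0 = 0.75 g/m²/day

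The stated 1 g/m²/day is reproduced only at the lower end of the plan's own range.

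**Step 2. The two readings above 1.5 m².** With no cap, daily dose = 1 g/m² × area. With a cap, the dose is 1.5 g/day and the dose per m² is as in Step 1.

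| Area (m²) | No cap: g/day | Excess over 1.5 g | Cap: g/m²/day |
|---|---|---|---|
| 1.5 | 1.50 | 0% | 1.00 |
| 1.75 | 1.75 | 17% (0.25 ÷ 1.5) | 0.857 |
| 2.0 | 2.00 | 33% (0.50 ÷ 1.5) | 0.75 |

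On either reading, one of the two statements in Section 5.7 is untrue for a participant above 1.5 m².

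**Step 3. Rounding at the limit.** Assume two equal doses. Then 1.5 g/day is 750 mg per dose, which lies midway between 700 and 800 mg, and no tie rule is given. The daily total is 2 × 700 = 1,400 mg or 2 × 800 = 1,600 mg. Equal rounded doses cannot give 1.5 g, and rounding up passes the limit. Unequal doses of 700 and 800 mg would sum to 1.5 g, but the plan does not provide for them.

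**Step 4. Per kg against per m².** The documents give no body sizes, so this step rests on assumed ones and on the Mosteller formula, area = √(kg × cm ÷ 3600).

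- 16 kg, 102 cm: area 0.673 m²; 673 mg ÷ 16 kg = about 42 mg/kg
- 32 kg, 138 cm: area 1.108 m²; about 35 mg/kg
- 50 kg, 160 cm: area 1.491 m²; about 30 mg/kg
- 70 kg, 176 cm: area 1.850 m²; 1,850 mg ÷ 70 kg = about 26 mg/kg with no cap

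From the smallest to the largest of these, the mg/kg value differs by a factor of about 42 ÷ 26 = 1.6. No single mg/kg dose reproduces 1 g/m²/day across the age range.

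**Step 5. Can eligible participants exceed 1.5 m²?** By the same formula, 50 kg and 162 cm gives √(50 × 162 ÷ 3600) = 1.50 m². The assumed 70 kg, 176 cm participant has a BMI of 70 ÷ 1.76² = 22.6, below the 27 named in Section 5.4. Participants above 1.5 m² can therefore be eligible. How many there will be cannot be derived from the documents.

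**The case against.** The strongest reply is that Section 5.7 is the operative dosing section and holds the only numeric rule. Nobody could dose from the Synopsis, which has no mg/kg figure. The opening sentence of Section 5.7 can be read as a cap on the per-m² dose, in which case no unrounded dose passes 1.5 g/day. Much of this stands. Up to 1.5 m² the section gives one defined dose apart from rounding, and a breach of the limit is not certain. But under the cap reading, "this is the dose we will be giving to our trial participants" is not true of larger participants, and the rounding problem remains.

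Several stronger inferences are tempting and are not supported.

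- **That the youngest would get about half the dose under a per-kg rule.** This needs an invented mg/kg value. For the 16 kg child, scaling from 1.5 g at 70 kg gives 16 × 1.5 ÷ 70 = 0.34 g, or 51% of 0.67 g. Scaling from 50 kg gives 16 × 1.5 ÷ 50 = 0.48 g, or 71%. After rounding, both become 400 mg/day against 600 mg/day, which is two thirds. The documents supply neither anchor.
- **That Section 6.7 sets a third basis.** Weight is an input to surface area, and height is recorded too, so item 8 is compatible with Section 5.7. Its wording only needs to match the reconciled rule.
- **That a result could not be tied to any dose.** There is one site and one research pharmacy. Section 5.7 (Study Medication Accountability) keeps dispensing records and records of drug used and returned, and Table 3 has height and weight at all five visits. Dispensed exposure can largely be reconstructed.
- **That the comparison is biased.** The Synopsis states the same basis for active and placebo GABA, so the ambiguity does not favour an arm.

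**Conclusion.** The point holds as an internal inconsistency in the dose rule. The Synopsis and Section 5.7 use dosing bases that are not interchangeable over ages 4 to 18. Within Section 5.7, the 1 g/m²/day dose and the 1.5 g/day limit agree only up to 1.5 m². At 2 m², the top of the plan's own adult range, the conflict amounts to 33% over the limit or, under a cap, a quarter less than the stated dose per m². Rounding at the limit gives 1.4 or 1.6 g/day.

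The limit and equivalence figures use only the plan's numbers, and the rounding figure adds the assumption of equal doses. The mg/kg comparison depends on assumed body sizes. What is affected is the instruction for larger participants and the description of the tested exposure, which bears on the safety objective. A reader might go on to infer that the trial tests no defined treatment, or that adolescents will be dosed beyond the limit. The documents establish neither.

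**What to change.** Reconcile the Synopsis and Section 5.7 on three matters: the dosing basis; how the 1.5 g/day limit relates to 1 g/m²/day above 1.5 m²; and rounding at the limit. Make the dose-adjustment wording in Section 6.7, item 8, match. The investigator and pharmacy decide which rule stands; this review does not propose one.

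Add to Section 9.0 a table of dispensed GABA exposure in mg/day, mg/kg and mg/m², by arm and age, derived from the pharmacy dispensing records and the height and weight already taken at every visit. Section 6.7, item 14, indicates that some participants have already completed visits, so the table should cover them as well.

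The cost is protocol wording and one derived table. No new measurement is needed.

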## 2) Subcutaneous GAD-alum

The Diamyd Drug Product (GAD-alum) is composed of the recombinant human GAD65 (rhGAD65) protein formulated in a sterile, non-pyrogenic phosphate buffered saline containing the aluminum hydroxide adjuvant, Alhydrogel, and will be provided by Diamyd Medical, Sweden (GAD-alum). The active ingredient, rhGAD65, is manufactured via a process involving expression in an insect cell line. The Drug product is supplied in a 3 mL glass vial with either 20µg Diamyd alum-formulated vaccine/mL or placebo. The dose volume is 0.5 mL for each subcutaneous administration. The vials have a slight overage to allow a withdrawal of 0.5mL. All dosing will take place in the hospital-based clinic, and handled only by trained, authorized study personnel.

All subjects will receive an injection of either GAD-alum or placebo at baseline (within 1 month after diagnosis), and a booster vaccine approximately 1 month later. The 20µg of GAD-alum (Diamyd Medical) is administered subcutaneously and, prior to exiting the clinic, the patient is observed for 1 hour post injection. The placebo injection has the equivalent components save, of course, the recombinant GAD, and is prepackaged in identical-appearing vials. The vials will be packaged into identical vial boxes. Both the vial box and the vial will be labeled with the same treatment number. Allocation of treatment to GAD-alum or placebo will be accomplished through Children's of Alabama Research Pharmacist.

The Diamyd Drug Product and Placebo Diamyd drug Product will be administered by the site personnel, and the administration will be documented in the site source documentation.

All vials of Diamyd and placebo will be kept between 2 and 8°C in a refrigerator that is behind a locked door in the Research Pharmacy to protect from unintended use. The temperature of the refrigerator is monitored constantly for accuracy. Any temperature deviations will be reported to Diamyd as soon as the site becomes aware of it. Vials should never be frozen, and any frozen vials should be rejected and is not allowed to be used clinically.

Diamyd product and placebo will be shipped from the distributor to the study site according to country specific laws and regulations. Diamyd product will not be offered to patients after the completion of the study. Participants will thereafter receive therapy at the discretion of the investigator.

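### Section 5.7 gives a GAD-alum vial strength and injection volume that multiply to 10 µg per injection, half the 20 µg dose the protocol states

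*Combined protocol and SAP*

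**What the plan says.** Section 5.7, part 2 (Subcutaneous GAD-alum), describes the product as follows: "The Drug product is supplied in a 3 mL glass vial with either 20µg Diamyd alum-formulated vaccine/mL or placebo". It then sets the injected volume at 0.5 mL ("Diamyd alum-formulated vaccine/mL or placebo. The dose volume is 0.5 mL for each subcutaneous administration") and repeats that volume when describing the vial: "The vials have a slight overage to allow a withdrawal of 0.5mL".

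The next paragraph of the same section says that 20 µg "of GAD-alum (Diamyd Medical) is administered subcutaneously". The rest of the protocol agrees with that dose:

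- The product name at the head of the synopsis is a 20 µg subcutaneous injection.
- The synopsis (Study Design) has the combination arm receiving GABA "plus 2 subcutaneous injections of 20" µg each.
- The synopsis (Description of Treatment Groups) describes one prime and one booster dose, "providing a total dose of 40" µg.
- Table 1 shows 20 µg at the prime and 20 µg at the boost for Group 1.

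Table 2 shows one injection at each of the two dosing visits.

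**The concern.** Section 5.7 is the operative dosing section and the only place that gives both a strength and a volume for GAD-alum. Those are the figures from which an injection is prepared. As written, they do not produce the dose stated elsewhere, including one paragraph later.

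Groups 1 and 2 both receive active GABA and differ only in whether the injection is GAD-alum or its placebo. The GAD-alum dose therefore defines what the combination arm tests beyond GABA alone. If the stated strength and volume were both correct, that arm would test half the stated dose, and a trial report quoting 20 µg per injection would be wrong. The product is also an investigational biologic given to children, so its preparation details should not be left to inference.

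**Working it through.** **Inputs, all from the protocol**

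| Quantity | Value | Where |
|---|---|---|
| Vial strength | 20 µg/mL | Section 5.7, part 2 (once) |
| Injected volume | 0.5 mL | Section 5.7, part 2 (twice: dose volume and vial withdrawal) |
| Stated dose per injection | 20 µg | Product name, synopsis, Table 1, Section 5.7 part 2 |
| Stated total dose | 40 µg | Synopsis |
| Injections per participant | 2, one per dosing visit | Section 6.2, Table 2 |
| Planned combination arm | 30 | Synopsis, Table 1 |

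**The plan's own total.** Total = dose × number of injections = 20 µg × 2 = 40 µg. This reproduces the synopsis, so the stated dose and stated total agree with each other.

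**Dose implied by strength and volume**

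- Per injection: 20 µg/mL × 0.5 mL = 10 µg.
- Over two injections: 10 µg × 2 = 20 µg.
- Ratio to the stated figures: 10/20 = 20/40 = 0.5.

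**What would reconcile the three numbers**

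- Holding dose and volume: 20 µg ÷ 0.5 mL = 40 µg/mL, that is, 20 µg per 0.5 mL.
- Holding dose and strength: 20 µg ÷ 20 µg/mL = 1.0 mL, twice the stated volume.
- Holding strength and volume: the dose is 10 µg per injection and 20 µg in total.

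**Whether the text already reconciles them**

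- Two injections or two vials per visit: no. Table 2 shows one injection at the prime and one at the boost, and no passage mentions a second vial.
- A larger withdrawal: not as written. The overage is described as slight and serves a 0.5 mL withdrawal.
- The 3 mL figure: this is the size of the glass vial. It is not a fill volume and does not change the injected volume.
- The site's own label: the list of label contents under Study Medication Accountability includes the drug name, directions for use, lot and expiry, but neither strength nor dose.

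**Extent.** The inconsistent description covers 30 × 2 = 60 planned active injections. This counts injections described inconsistently; it does not count injections known to be wrong.

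**The case against.** The best counter-argument is that this is a unit slip with little practical consequence. The planned dose is not in real doubt: 20 µg appears in the product name, the synopsis, Table 1 and Section 5.7 itself, and the 40 µg total agrees. Only the per-mL strength disagrees, and it appears once. The product is named as a 20 µg injection and the vial is sized for a single 0.5 mL withdrawal, so 20 µg per 0.5 mL is the natural reading. Vials arrive pre-formulated, and no described site step calculates a volume from the strength. If the strength is the misprint, drawing up 0.5 mL delivers 20 µg anyway. Endpoint, comparisons and power are untouched.

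Most of this stands. The intended dose is 20 µg, the strength is the likeliest error, and no under-dosing is shown. It remains an inference, however. If the supplied product really is 20 µg/mL, a site following the stated 0.5 mL would give 10 µg. Only the supplier's label or supply records can exclude that, and the protocol does not reproduce them. A probable misprint in the operative dosing section still has to be confirmed and corrected.

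**Conclusion.** The concern holds. As written, Section 5.7 specifies 10 µg per injection and 20 µg in total, against a stated 20 µg and 40 µg: exactly half. The arithmetic uses only the protocol's own figures and one injection per dosing visit, as Table 2 shows.

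What remains open is which of the three numbers (strength, volume or dose) is wrong. The pattern of repetition points to the strength, but the document does not settle it. The finding is an error in the written specification. It is not evidence about what participants received, and it has no bearing on the power calculation.

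**What to change.** Have the research pharmacy check the supplier's label or supply documents, then correct Section 5.7 so that strength times volume equals the dose:

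- **If 0.5 mL is right and the dose is 20 µg:** state the strength as 20 µg per 0.5 mL (40 µg/mL).
- **If 20 µg/mL is right and 20 µg is intended:** change the volume to 1.0 mL and correct the sentence on vial overage to match. The placebo volume must change too, so that the injections stay indistinguishable.
- **If the label shows that 10 µg was delivered:** restate the tested dose as 10 µg per injection and 20 µg in total in the synopsis, Table 1 and Section 5.7, and report it as such.

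A minor wording point on the other drug can be tidied in the same edit. The synopsis has "oral GABA, dosed per kg, twice daily for 12 months", while Section 5.7, part 1, doses by body surface area at 1 g/m²/day, not exceeding 1.5 g/day, and says "this is the dose we will be giving to our trial participants". The synopsis should carry the Section 5.7 rule. The GAD-alum finding does not depend on this.

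The cost is one label check and a short text correction. Design, sample size and analysis are unchanged.
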